Previous work has shown that the HSD3B1 genotype does not classically affect circulating DHEA-S levels, but rather affects tissue androgen levels (4, 8, 9). Based on our preliminary data and published reports (5), we anticipate that the maximal effect of DHEA will be observed in patients with the responsive genotype (4) and low DHEA-S levels (4) (**Table 1**). Because the homozygous HSD3B1(1245) AA genotype and heterozygous AC genotype in severe asthma populations are similar in lung function (4), and because the CC genotype is uncommon (12%; **Table 2**), we will focus on the “optimal response” cohort (AA/AC genotype & low DHEA-S levels). If we are successful, additional studies will be performed in subsequent, larger trials. Steady state levels in the pilot study were ~ 725 µg/dL (5). Therefore, we will study 100 mg of DHEA (10,11).

Table 1. Predicted biomarker response (based on previously published work from our group)(4,5).

	Serum DHEA-S levels (µg/dL)	
	<90 in males or <45 in females	≥90 in males or ≥45 in females
HSD3B1(1245) genotype		
CC	Intermediate Response	Poor Response
AA or AC	Optimal Response	Intermediate Response

2 CLINICAL SIGNIFICANCE

Severe asthma only accounts for ~10% of all asthma in the United States, but it accounts for nearly half of the annual mortality and cost of the disease (12-16). Estimates are that severe asthma takes over

1,000 lives per year, and that the annual financial burden of severe asthma may be several billion dollars in the United States alone. Important improvements in asthma outcomes have been realized with antibody-based

Table 2: HSD3B1(1245) genotype distribution in SARP I, II & III

Genotype	American Indian/ Alaskan Native	Asian	African American	White/ Caucasian	Hispanic	Other
AA - n(%)	4 (80)	30 (83)	375 (77)	411 (46)	22 (52)	27 (63)
AC - n(%)	1 (20)	5 (14)	105 (22)	386 (43)	18 (43)	13 (30)
CC - n(%)	0 (0)	1 (3)	6 (1)	100 (12)	2 (5)	3 (7)

therapies (for example, 17-19). However, these therapies are primarily effective for specific subpopulations of the Th-lymphocyte Type 2-high (“T2-high”) asthma population, are normally not indicated in the “T2 low” population (17-21) and are expensive. Here, we propose to investigate potentially less expensive, less invasive, personalized approaches to managing certain severe patients, particularly including those who are not candidates for, or have failed, conventional severe asthma therapies and biological approaches.

3 STUDY OBJECTIVES

3.1 PRIMARY OBJECTIVE:

- Determine if slow-release DHEA in patients with asthma improves quality of life based on ACQ/ACT scoring.

3.2 SECONDARY OBJECTIVE:

- Determine if slow-release DHEA increases FEV₁ in patients with asthma.
- Determine if SR DHEA in patients with asthma increases the change in pulmonary functions post maximum bronchodilator challenge.
- Determine if slow-release DHEA in patients with asthma decreases FeNO.
- Evaluate the safety and tolerability of DHEA in asthma.
 - Safety outcomes include changes in:
 - Adverse events (AEs)
 - Serious adverse events (SAEs)
 - Pulmonary function (FEV₁, FVC, FEV₁/FVC, FEF25-75)

(An asthma exacerbation (physician decision to treat) will be considered an event of particular interest. Exacerbations not admitted to the hospital will be considered an AE. Exacerbations requiring admission will be considered a SAE.)

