6 SCHEDULED EVENTS

Assessments and Procedures	Visit 0	MCT	Visit 1	Visit 2	Visit 3	Visit 4	Visit 5	Visit 6
	Screening Day 0	Anytime between days 1-7; at least 3 days prior to Visit 1	Day 7 ± 3 days	Day 21 ± 3 days (phone visit)	Day 35 ± 3 days	Day 63 ± 3 days	Day 77 ± 3 days (phone visit)	Day 91 ± 3 days
Informed consent	X							
Medical history and demographics	X							
Concomitant medications	X		X	X	X	X	X	X
Review inclusion/exclusion criteria	X							
Asthma Control Test (ACT) & Asthma Control Questionnaire (ACQ)	X		X	X	X	X	X	X
Height	X							
Weight, pulse oximetry, vital signs	X	X	X		X	X		X
Urine pregnancy test (when applicable)	X	X	X		X	X		X
Urine cotinine test	X							

Assessments and Procedures	Visit 0	MCT	Visit 1	Visit 2	Visit 3	Visit 4	Visit 5	Visit 6
	Screening Day 0	Anytime between days 1-7; at least 3 days prior to Visit 1	Day 7 ± 3 days	Day 21 ± 3 days (phone visit)	Day 35 ± 3 days	Day 63 ± 3 days	Day 77 ± 3 days (phone visit)	Day 91 ± 3 days
Prostate specific antigen test ¹ (when applicable)	X							
Spirometry with bronchodilator response (maximum bronchodilator)	X							
Spirometry. If ≥ 10% decrease in FEV ₁ from baseline, give bronchodilator and measure response			X		X	X		X
Methacholine Checklist ^a		X						
Methacholine Challenge Test (MCT) (Asthma Participants Only) ^a		X						
FeNO	X		X		X	X		X
Abbreviated physical exam	X		X		X	X		X
Blood draw	X		X		X	X		X
DHEA/placebo capsules dispensed in labeled bottle			X			X		
Collect any unused DHEA/placebo capsules					X			X
Adverse events	X	X	X	X	X	X	X	X
Give Dosing & Symptom Diary			X			X		

¹ This test is for male subjects only. The prostate specific antigen is a protein made by the prostate and found in blood. If the result of this test is >4 nanograms per milliliter, subjects will be informed they are unable to participate in the study. We will also call them prior to their next visit to let them know and recommend that they follow-up with their regular primary care physician.

Assessments and Procedures	Visit 0	MCT	Visit 1	Visit 2	Visit 3	Visit 4	Visit 5	Visit 6
	Screening Day 0	Anytime between days 1-7; at least 3 days prior to Visit 1	Day 7 ± 3 days	Day 21 ± 3 days (phone visit)	Day 35 ± 3 days	Day 63 ± 3 days	Day 77 ± 3 days (phone visit)	Day 91 ± 3 days
Collect Dosing & Symptom Diary					X			X

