7 DESCRIPTION OF EVENTS

Medical history and demographics, height, weight and vital signs

Relevant medical history, including history of current disease, spirometry results, other pertinent respiratory history, and information regarding underlying diseases will be recorded. Demographic and baseline clinical characteristics including age, gender, and race will be recorded. Pulse oximetry, height (at screening only) and weight will be measured, as well as vital signs (blood pressure, temperature, heart rate and respiration rate).

Concomitant medications

All concomitant medications and concurrent therapies will be documented at visit 0. Dose, route, unit frequency of administration, and indication for administration and dates of medication will be captured for the 30 days prior to screening and during the study. The document will be reviewed and addended (if needed) at each visit.

Asthma questionnaires

Subjects will be asked to complete two questionnaires: the Asthma Control Test (ACT) and the Asthma Control Questionnaire (ACQ).

- The ACT is a validated asthma assessment tool used to assess asthma symptoms over a 4-week period. Each item on the ACT has a possible score ranging from 0 to 5, and the total score is used to determine asthma control.
- The ACQ includes six questions on symptoms, activity limitation and beta2-agonist use, with an optional assessment on airway caliber over a 7-day period. Each question is scored from 0 (well controlled) to 6 (extremely poorly controlled) with the total score being the average of the questions.

Urine pregnancy test

A urine pregnancy test will be performed at Visits 0 and Visit 1 (if not the same day as screening visit) if the subject is a female of child bearing potential.

Urine cotinine test

A urine cotinine test will be performed at Visit 0 for all subjects to measure cotinine levels.

Prostate specific antigen test

Blood will be obtained from male subjects for PSA because administration of supplemental DHEA in people with prostate cancer could theoretically result in a flare-up of their prostate cancer.

Spirometry with maximum bronchodilator response

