8 DESCRIPTION OF VISITS

Below are the visits and the interventions that may occur at each of the visits. In addition to the following scheduled visits, we are also including an unscheduled visit that may be used for any reason when a subject needs to return to the study site to complete study activities.

Visit 0 (Screening Visit)

1. Review the study with the subject and obtain written informed consent and HIPAA authorization
2. Assign the subject a unique subject id number
3. Complete asthma control test and asthma control questionnaire
4. Record demographics and other baseline data

5. Record medical and surgical history, including a history of asthma, diagnosis date, and asthma signs and symptoms
6. Record concomitant medications
7. Review inclusion/exclusion criteria
8. Measure and record height and weight without shoes
9. Perform and record vital signs, including blood pressure after the subject has been seated for 5 minutes
10. Perform and record oximetry
11. Perform abbreviated physical exam
12. Obtain urine to perform urine pregnancy test (when applicable) and urine cotinine test
13. Obtain blood for prostate specific antigen test (when applicable)
14. Perform spirometry with maximum bronchodilator response
15. Perform FeNO
16. Obtain blood
17. Record any adverse events (AEs) that may have occurred since signing consent
18. Schedule MCT or Visit 1

MCT Visit, if needed (Anytime between days 1-7, must be at least 3 days prior to Visit 1)

1. Confirm ongoing consent to participate
2. Collect urine for pregnancy test if applicable
3. Record vital signs and weight
4. Complete MCT checklist
5. Perform and record MCT
6. Confirm eligibility criteria
7. Record adverse events
8. Schedule Visit 1

Visit 1 (Day 7 ± 3)

1. Complete asthma control test and asthma control questionnaire
2. Review and record any changes to concomitant medications
3. Record any adverse events (AEs) that may have occurred since last visit
4. Measure and record weight without shoes
5. Perform and record vital signs, including blood pressure after the subject has been seated for 5 minutes
6. Perform and record oximetry
7. Perform abbreviated physical exam
8. Obtain urine to perform urine pregnancy test (when applicable)
9. Perform spirometry
10. Perform FeNO
11. Obtain blood
12. Give subject a dosing and symptom diary and instructions on dosing intervals
13. Randomize to receive placebo or DHEA-S
14. Send home with 28 days of DHEA-S or placebo capsules
15. Schedule visit 2

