Visit 2 (Day 21 ± 3) phone visit

1. Complete asthma control test and asthma control questionnaire
2. Review and record any changes to concomitant medications
3. Record any adverse events (AEs) that may have occurred since last visit
4. Schedule visit 3

Visit 3 (Day 35 ± 3)

1. Complete asthma control test and asthma control questionnaire
2. Review and record any changes to concomitant medications
3. Record any adverse events (AEs) that may have occurred since last visit
4. Review inclusion/exclusion criteria
5. Measure and record weight without shoes
6. Perform and record vital signs, including blood pressure after the subject has been seated for 5 minutes
7. Perform and record oximetry
8. Perform abbreviated physical exam
9. Obtain urine to perform urine pregnancy test (when applicable)
10. Perform spirometry
11. Perform FeNO
12. Obtain blood
13. Collect any unused capsules from visit 1
14. Collect dosing and symptom diary
15. Schedule visit 4

Visit 4 (Day 63 ± 3)

1. Complete asthma control test and asthma control questionnaire
2. Review and record any changes to concomitant medications
3. Record any adverse events (AEs) that may have occurred since last visit
4. Measure and record weight without shoes
5. Perform and record vital signs, including blood pressure after the subject has been seated for 5 minutes
6. Perform and record oximetry
7. Perform abbreviated physical exam
8. Obtain urine to perform urine pregnancy test (when applicable)
9. Perform spirometry
10. Perform FeNO
11. Obtain blood
12. Give subject a dosing and symptom diary and instructions on dosing intervals
13. Randomize to receive placebo or DHEA-S (will enter whatever did not receive in visits 1-3)
14. Send subject home with 28 days of 100 mg DHEA-S or placebo capsules to take daily
15. Schedule visit 5

Visit 5 (Day 77 ± 3) phone visit

1. Complete asthma control test and asthma control questionnaire

2. Review and record any changes to concomitant medications
3. Record any adverse events (AEs) that may have occurred since last visit
4. Schedule visit 6

Visit 6 (Day 91 ± 3)

1. Complete asthma control test and asthma control questionnaire
2. Review and record any changes to concomitant medications
3. Record any adverse events (AEs) that may have occurred since last visit
4. Measure and record weight without shoes
5. Perform and record vital signs, including blood pressure after the subject has been seated for 5 minutes
6. Perform and record oximetry

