13 SAFETY ASSESSMENTS

The monitoring in place for assessing the subject's responses will ensure that any untoward change in physiologic status is immediately known.

This includes the following:

1. Measuring pulmonary function at the beginning of each visit and measuring bronchodilator response if there is a drop $\geq 10\%$ from baseline.
2. Obtaining ACT scores at each visit to assess subjects' asthma control.
3. Performing an abbreviated physical exam at all visits.
4. Checking vital signs, including pulse oximetry, to ensure the subject is at their baseline.
5. Asking about interim history to ensure the subject has not had an asthma exacerbation since the previous visit.

As a result of the study design, subjects will be monitored on a case-by-case basis by the study coordinator. The experimental design has each subject extensively monitored; any manner of medical intervention is immediately available, and the appearance of any suspected untoward effect will result in cessation of protocol procedures if decided by the principal investigator.

Any applicable safety concerns will be reported as described above.

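### The secondary objective on maximum bronchodilator response has no scheduled on-treatment measurement

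*Protocol*

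**What the plan says.** - **Objective.** Protocol section 3.2 lists as a secondary objective: "Determine if SR DHEA in patients with asthma increases the change in pulmonary functions post maximum bronchodilator challenge". A separate objective in the same list asks whether DHEA raises FEV1.
- **Schedule, maximum test.** In the section 6 table the row "Spirometry with bronchodilator response (maximum bronchodilator") is marked at Visit 0 (screening) only.
- **Schedule, later visits.** A second spirometry row covers Visits 1, 3, 4 and 6. There the instruction to "give bronchodilator and measure response" applies only when FEV1 is down by at least 10% from baseline. It does not say that the bronchodilator dosing is maximum.
- **Visit lists.** In section 8, Visit 0 reads "Perform spirometry with maximum bronchodilator response". The lists for Visits 1, 3, 4 and 6 read only "Perform spirometry". Randomisation takes place at Visit 1, and subjects cross to the other treatment at Visit 4.
- **Procedure description.** Section 7, under "Spirometry with maximum bronchodilator response", describes pre- and post-bronchodilator FEV1 and names no visit.
- **Safety.** Section 13 repeats the condition: "measuring bronchodilator response if there is a drop" of 10% or more.

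**The concern.** The objective is a treatment comparison, so it needs the same measurement under both treatments. The only scheduled maximum-bronchodilator test comes before either treatment has started. It serves eligibility: showing reversibility (section 5.1) and deciding whether a methacholine challenge is needed (footnote to the section 6 table).

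The only on-treatment bronchodilator data would come from the triggered tests, and these are selected on an outcome. If DHEA raises FEV1, fewer DHEA-period visits meet the trigger, and the subjects who still meet it are not comparable with those who meet it on placebo. A comparison built on them would be sparse and, in that case, biased. The within-subject contrast that a cross-over is meant to provide would exist only for subjects whose FEV1 fell at both Visit 3 and Visit 6.

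The measure is not incidental. Section 9 reports that the team's earlier two-week pilot found a significant improvement in post-bronchodilator FEV1.

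**Working it through.** **Step 1. Count the planned tests.** The protocol gives no figure tied to this objective, so there is nothing to reproduce. From the section 6 table and the section 8 lists:

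| Visit | Position in the cross-over | Unconditional maximum-bronchodilator test |
|---|---|---|
| 0 (Day 0) | screening | 1 |
| 1 (Day 7) | randomisation, before period 1 dosing | 0 |
| 3 (Day 35) | end of period 1 | 0 |
| 4 (Day 63) | before period 2 dosing | 0 |
| 6 (Day 91) | end of period 2 | 0 |

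The comparison needs Visits 3 and 6, and both entries are zero. The table, the visit lists and the safety section agree with one another; the objective is the one that does not fit.

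**Step 2. Look for another source.** The text in section 7 on pre- and post-bronchodilator FEV1 stands under the heading of the Visit 0 procedure and names no other visit. The unscheduled visit in section 8 is not a planned measurement. Section 17 mentions mixed-effects models. These can use a subject with only one value, but subjects without a fall are never tested, so a model could only extrapolate to them.

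**Step 3. Illustrate how many triggered tests there might be.** The protocol gives 30 subjects (section 4.2) and a 10% trigger. It gives no SD or within-subject correlation and does not define the baseline for the trigger. All of the following are therefore assumptions: percentage change in FEV1 is normal with SD 6% to 12%, there is no dropout, and DHEA shifts the mean by 0, 3 or 5 percentage points.

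P(tested) = Φ((−10 − shift) / SD); expected number = 30 × P.

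| Shift | SD 6 | SD 8 | SD 10 | SD 12 |
|---|---|---|---|---|
| 0 | 4.8%, 1.4 | 10.6%, 3.2 | 15.9%, 4.8 | 20.2%, 6.1 |
| +3 | 0.5 | 1.6 | 2.9 | 4.2 |
| +5 | 0.2 | 0.9 | 2.0 | 3.2 |

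Entries are numbers out of 30; the first row also gives the probability. Because half the design crosses in each direction, 30 observations on one treatment means Visits 3 and 6 pooled.

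Number of 30 tested at both Visit 3 and Visit 6 (bivariate normal, no shift at either visit):

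| Correlation | SD 6 | SD 8 | SD 10 | SD 12 |
|---|---|---|---|---|
| 0 | 0.1 | 0.3 | 0.8 | 1.2 |
| 0.5 | 0.3 | 1.1 | 1.9 | 2.7 |
| 0.9 | 0.9 | 2.2 | 3.5 | 4.6 |

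One of the two visits is always on DHEA. With a shift of +3 at that visit only, the range falls from 0.07–4.6 to about 0.02–3.6 (lowest at SD 6 and correlation 0, highest at SD 12 and correlation 0.9).

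**The case against.** The strongest points on the other side are these.

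1. *The bias argument attacks an analysis nobody proposed.* Section 13 lists triggered bronchodilator testing as a safety assessment, and no section says those data will answer the objective. This is fair. The basic defect is that no on-treatment measurement is planned; the selection argument explains why the triggered data cannot fill the gap.
2. *Selection differs by treatment only if DHEA changes FEV1.* Correct, and the bias statement is conditional on that. With no effect on FEV1 the trigger would work alike under both treatments, but the data would still cover only subjects who had a fall.
3. *The counts rest on assumed inputs.* They do, and they are shown only as an illustration. The zeros in Step 1 need no assumption.
4. *This is an omission rather than a contradiction, and section 7 says without visit limits that post-bronchodilator FEV1 is measured.* The label matters little. Section 7 is at most ambiguous, whereas the schedule and the visit lists are explicit.
5. *It is one secondary objective in a 30-subject pilot.* This stands and limits the weight of the point. It does not make the objective answerable.

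A separate analysis plan does not help, because it cannot schedule a test.

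**Conclusion.** The point holds, with high confidence. As scheduled, the trial collects no unconditional maximum-bronchodilator measurement under either treatment, so this secondary objective cannot be answered. That conclusion follows from the text alone. Any comparison using the triggered tests would be restricted to subjects with an FEV1 fall and, if DHEA raises FEV1, biased by differing selection. It would probably also be very small: under the assumed SDs, at most about 6 of 30 at a visit and fewer than 5 at both.

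The ACQ/ACT, FEV1, FeNO and safety objectives are unaffected. This should be fixed, ideally before more subjects finish a period, since measurements missed in enrolled subjects cannot be recovered.

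**What to change.** Reconcile section 3.2 with sections 6, 7, 8 and 13 in one of two ways.

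- **Option A.** Remove this objective, keep the existing FEV1 objective as the lung-function comparison, and state that bronchodilator measurements triggered by an FEV1 fall are for safety and not for comparing treatments. *Cost:* a protocol amendment, with no new procedures. The sponsor should know that this drops the measure closest to the pilot result cited in section 9.
- **Option B, only if the sponsor wants to keep the objective.** Schedule the maximum-bronchodilator test for every subject at Visits 3 and 6, done the same way each time and whether or not FEV1 has fallen. State that the preparation described in section 7 for reversibility testing applies at those visits too. *Cost:* two more tests per subject at visits that already include spirometry, with longer visits and more burden on participants.

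Option A is sufficient to remove the inconsistency.

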along with the IRB, the study's Steering Committee, and the NHLBI Program Officer of any serious AEs. Procedures and requirements for prompt reporting of AEs and unanticipated problems involving risk to subjects or others have been established by our IRB and will be adhered to for all aspects of this project. Any member of the study team will report any unexpected event or problem and any AE, either serious or non-serious, to the PI immediately upon discovery. The PI will then proceed to report the event within the specified timeframes mandated by the DSMB Charter, the IRB and the NHLBI. Any non-serious AE, either study or not study related, can be reported by the research team at the date of the next continuing review. Current regulations require that any AE that is (1) unexpected (in terms of nature, severity, or frequency) given (a) the research procedures that are described in the study-related documents, and (b) the characteristics of the subject population being studied, (2) related or possibly related to study participation, AND (3) suggesting that the research places subjects or others at greater risk of harm than was previously known must be reported to the IRB within 5 business days. A SAE that is non-study related can be reported at the next continuing review.

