14.1 ADVERSE EVENT ASSESSMENT

All adverse events will be reported to the Indiana University IRB and FDA as required per their adverse event reporting policies. At the time of the annual review of the study, adverse events will be reported as per the Indiana University HRPP Reportable Events Policy and Guidance. An Adverse Reaction Reporting Form will be completed for any serious and unexpected adverse reaction associated with the study, and the Indiana University IRB will be notified per IU HRPP Reportable Events Policy and Guidance.

An IND safety report will be submitted to the FDA for an event that is a (1) suspected adverse reaction, (2) serious, and (3) unexpected, per FDA guidance.

Suspected adverse reaction means any adverse event for which there is a reasonable possibility that the drug caused the adverse event. For the purposes of IND safety reporting, 'reasonable possibility' means there is evidence to suggest a causal relationship between the drug and the adverse event.

An adverse event or suspected adverse reaction is considered "serious" if, in the view of either the investigator or sponsor, it results in any of the following outcomes: Death, a life-threatening adverse event, inpatient hospitalization or prolongation of existing hospitalization, a persistent or significant incapacity or substantial disruption of the ability to conduct normal life functions, or a congenital anomaly/birth defect. Important medical events that may not result in death, be life-threatening, or require hospitalization may be considered serious when, based upon appropriate medical judgment, they may jeopardize the patient or subject and may require medical or surgical intervention to prevent one of the outcomes listed in this definition.

An adverse event or suspected adverse reaction is considered "unexpected" if it is not listed in the investigator brochure or is not listed at the specificity or severity that has been observed; or, if an investigator brochure is not required or available, is not consistent with the risk information described in the protocol.

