14.3 ADVERSE EVENT REPORTING

- Every event that is reported to either the PI or the designated research associates by the subject or medical staff caring for the subject and which meets the criteria will be documented.
- An AE report will be generated for each event and each report will include: (1) description of the event; (2) when it was reported; (3) severity; and (4) a determination of attribution.
- All SAE's will be reported once the event has been verified, and determination of attribution has been completed in accordance with IU IRB reporting requirements and DSMB requirements. All other AEs will be reported according to the IU IRB reporting requirements.

DSMB requirements are that SAE's be reported to the board within 24 hours of learning of the confirmed event. DSMB will proceed to review, discuss and convey recommendations.

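### Section 3.2 classes an asthma exacerbation as AE or SAE by hospital admission alone, which contradicts the seriousness criteria in Sections 14 and 14.1

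*Protocol*

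**What the plan says.** Section 3.2 lists AEs and SAEs as separate safety outcomes. In a parenthesis below that list it states: "An asthma exacerbation (physician decision to treat) will be considered an event of particular interest". The seriousness rule follows at once: "Exacerbations not admitted to the hospital will be considered an AE. Exacerbations requiring admission will be considered a SAE". It has no clause for events that are serious on other grounds and no reference to Section 14.

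Section 14 says that AEs and SAEs are defined by FDA and OHRP guidelines, with no exception for exacerbations. Section 14.1 then calls an event serious if "it results in any of the following outcomes: Death, a life-threatening adverse event, inpatient hospitalization or prolongation of existing hospitalization", and adds incapacity and congenital anomaly. It also provides that "Important medical events that may not result in death, be life-threatening, or require hospitalization may be considered serious when, based upon appropriate medical judgment". That judgment turns on danger to the subject and on whether intervention may be needed to avert a listed outcome.

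The label affects reporting. Under Section 14.3, SAEs must "be reported to the board within 24 hours of learning of the confirmed event". Under Section 12, "Any non-serious AE, either study or not study related, can be reported by the research team at the date of the next continuing review".

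**The concern.** Admission is one route to seriousness in Section 14.1, but Section 3.2 treats it as the only route. Section 3.2 has a branch for admitted and a branch for non-admitted exacerbations, so it leaves no room for a further criterion. It also sets AE against SAE, so AE there can only sensibly mean non-serious.

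Two things are at stake. The SAE count is a stated safety outcome and would be wrong if Section 3.2 were followed to the letter. The 24-hour notice to the DSMB is tied to the SAE label, so a severe exacerbation without admission could miss it. An exacerbation is a foreseeable serious event in an asthma trial, and Section 9 itself names breathing difficulty as a risk of withholding beta-agonists before visits. The classification of its most severe forms should not depend on which section the site consults.

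**Working it through.** No arithmetic applies: the point is a conflict between two definitions, and neither uses a rate, sample size or error level. The check is to take each kind of exacerbation through both rules.

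| Exacerbation (physician decided to treat) | Section 3.2 | Section 14.1 | Agree? |
|---|---|---|---|
| Requires admission | SAE | Serious (hospitalization) | Yes |
| Not admitted, no other criterion met | AE | Not serious | Yes |
| Not admitted, life-threatening, treated and discharged | AE | Serious | No |
| Not admitted, fatal under treatment before admission | AE | Serious | No |
| Not admitted, important medical event on medical judgment | AE | May be serious | Conflict if judged serious |

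The first two rows will cover most exacerbations, and there the sections agree. The third and fourth rows are direct contradictions. The fifth is conditional, because Section 14.1 leaves it to judgment and Section 3.2 allows no judgment.

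Next, is there a rule of precedence? Section 3.2 does not say that it replaces Section 14.1. Section 14.1 does not say that it overrides Section 3.2. Section 12 has AEs categorized as serious or non-serious but gives no rule for exacerbations. The conflict is therefore unresolved in the text.

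Last, which consequences depend on the label?

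- SAE count (Section 3.2): depends on it.
- DSMB report within 24 hours (Section 14.3): depends on it.
- SAE notification to the PI and Steering Committee (Section 12): depends on it. However, every AE, serious or not, already goes to the PI immediately.
- IRB report within 5 business days (Section 12): does not depend on it. The test is unexpected, related or possibly related, and suggesting greater risk.
- IND safety report within 7 calendar days (Section 14.1): does not depend on the Section 3.2 label. The trigger is an unexpected fatal or life-threatening suspected adverse reaction.
- Report of deaths within 30 days of intervention to the IRB (Section 14.1): does not depend on it.

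**The case against.** The strongest reply is that Section 3.2 offers a working default in a parenthesis within the objectives, while the governing definitions are in Section 14. Every SAE is also an AE, so calling a non-admitted exacerbation an AE need not deny that it is serious. A careful site would apply Section 14.1 anyway. The protocol also has safeguards: the DSMB Chair adjudicates AEs, all AEs are graded (Grade 4 for life-threatening or disabling events, Grade 5 for death), and the PI hears of each one immediately.

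Much of this stands. It shows that misfiling is possible but not certain. It does not reconcile the sections: Section 3.2 contrasts AE with SAE and names no other criterion, and adjudication corrects a label only once the event has reached the adjudicator.

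A reader might also infer more than the protocol supports:

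- *That any death from asthma outside hospital becomes an AE.* Section 3.2 defines an exacerbation by a physician's decision to treat. An untreated death may fall outside its rule, and Section 14.1 would then make it serious directly.
- *That reporting to the DSMB could be delayed by close to a year.* This joins two separate clocks: continuing review, which Section 12 mentions in a paragraph largely about IRB procedures, and the DSMB's minimum of one meeting per year. Section 12 also says that the DSMB meets regularly to review all AEs.
- *That the 7-day IND report would be lost.* Its trigger does not refer to Section 3.2.
- *That the SAE rate would be wrong by a known amount.* One event in 30 subjects is 1/30 = 3.3 percentage points, but the protocol gives no event rate, so this is not an estimate of error.
- *That the SAE label always speeds reporting.* Section 12 lets an SAE unrelated to the study wait for continuing review at the IRB.

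**Conclusion.** The contradiction is real and lies in the wording. Section 3.2 gives one answer and Section 14.1 another for a treated life-threatening exacerbation without admission and for a death under treatment before admission. They can also differ on a non-admitted important medical event. Section 3.2 states an incorrect rule; this is not a detail left for another document.

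Its practical size is limited. It affects the SAE count and the 24-hour DSMB report, and only for severe exacerbations that do not lead to admission. Such events should be rare with 30 subjects and two 28-day treatment periods, and neither a delay nor a rate can be put on them from this protocol. The conclusion rests on two readings: that AE in Section 3.2 means non-serious because it is set against SAE, and that a site may follow the specific rule as written. The first is the only workable reading of that sentence. The second is plausible but not shown. The point does not touch randomization or the efficacy analysis.

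**What to change.** Reconcile the sections by replacing the two classification sentences in Section 3.2 with text such as: *An asthma exacerbation is recorded as an event of particular interest. It is an SAE if it meets any seriousness criterion of Section 14.1, admission being one of them; otherwise it is a non-serious AE.* Align the exacerbation field in the study database (Section 16.9) so that seriousness is recorded against each criterion and not derived from admission.

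The cost is a short amendment and one change to the data form. It needs no additional visits or staff and does not alter treatment. The SAE count may be slightly higher than under the present wording.
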